15.1 Conflicts of Interest

[name] will serve as an unpaid consultant on the study. He holds the patent rights to J591 and has served as a paid consultant to BZL Biologics (company that has assisted in the production of the J591 monoclonal antibody). He will have no access to any of the study data other than the blinded material (circulating tumor cells and archived tissue slides) on which some of his lab personnel may perform PSMA staining. He will have no role in screening of subjects, obtaining informed consent, treatment of the subjects, or analysis and reporting of the data.

16. Funding

This protocol has been initiated with WCMC funding as well as funding via the WCMC CTSC. Funds from WCMC have been and will be supplemented through past grants from the Cancer Research Institute, the David H. Kock Foundation, and the National Cancer Institute. Part of the Study Chair's funding through a K12 mechanism (KL2 RR024997-01 (PI: [name]) K12 Clinical & Translational Research Training Scholars Award) and Prostate Cancer Foundation Young Investigator's award will cover his time and effort in the development of the protocol. The study will be performed at the WCMC CTSC through funds via the WCMC CTSA (UL1 RR024996). Additional study sites have preferentially been chosen because of available CTSA funding. Some of the correlative studies (adrenal androgen levels, plasma markers of hemostasis, fibrinolysis, and angiogenesis) will be performed in the WCMC CTSC core lab and will be funded via the CTSA. The user ID/password protected/encrypted web-based database will also be built and run by WCMC CTSC personnel funded via the CTSA.

Additional funding for the WCMC site will be obtained through the Department of Defense (via a DOD Prostate Cancer Research Program Clinical Trial Award (Funding Opportunity Number W81XWH-08-PCRP-CTA, PC081664). There will be strict non-overlapping budgets, as funds are available from multiple sources. Other sites will be funded via their CTSA and supplemented by the WCMC Urologic Oncology Research Fund.

17. Additional Study Sites

APPENDIX A

Performance Status Criteria

ECOG Performance Status Scale		Karnofsky Performance Scale	
Grade	Descriptions	Percent	Description
0	Normal activity. Fully active, able to carry on all pre-disease performance without restriction.	100	Normal, no complaints, no evidence of disease.
		90	Able to carry on normal activity; minor signs or symptoms of disease.
1	Symptoms, but ambulatory. Restricted in physically strenuous activity, but ambulatory and able to carry out work of a light or sedentary nature (e.g., light housework, office work).	80	Normal activity with effort; some signs or symptoms of disease.
		70	Cares for self, unable to carry on normal activity or to do active work.
2	In bed <50% of the time. Ambulatory and capable of all self-care, but unable to carry out any work activities. Up and about more than 50% of waking hours.	60	Requires occasional assistance, but is able to care for most of his/her needs.
		50	Requires considerable assistance and frequent medical care.
3	In bed >50% of the time. Capable of only limited self-care, confined to bed or chair more than 50% of waking hours.	40	Disabled, requires special care and assistance.
		30	Severely disabled, hospitalization indicated. Death not imminent.
4	100% bedridden. Completely disabled. Cannot carry on any self-care. Totally confined to bed or chair.	20	Very sick, hospitalization indicated. Death not imminent.
		10	Moribund, fatal processes progressing rapidly.
5	Dead.	0	Dead.

APPENDIX B

Stopping Rules (from phase 2 single-dose study, to be used as a guideline for DSMB reporting)

In the initial portion of the single-dose phase II study of ^{177}Lu -J591 for men with metastatic CRPC, the FDA required notification with a hold on further enrollment pending review if any of the below criteria were met. For the current study, the DSMB must be notified when any of the below stopping rules occur. Should >1 subject within the initial 9 experience any of the following, further enrollment will be held until DSMB review and FDA permission for continuation is given.

Hematologic

[figure not shown]
- Grade 4 thrombocytopenia that persists for ≥ 14 days after therapy
- Grade 4 thrombocytopenia that requires > 2 platelet transfusions over a 14 day period (note that multiple units of platelet products given together are considered a single transfusion)
- Grade 3 thrombocytopenia persisting > 30 days
- Grade 4 neutropenia that requires growth factor support for more than 14 days
- Grade 3 neutropenia that persists > 30 days
- Febrile neutropenia

Non-hematologic

- Any \geq Grade 3 non-hematologic toxicity considered by the investigator to be related to study drug (radiolabeled J591)

The NCI Common Toxicity Criteria for adverse events (CTCAE) version 4.0 will be utilized.

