Two independent phase I clinical trials have been performed at WCMC using ⁹⁰Y or ¹⁷⁷Lu linked via a DOTA chelate to huJ591 in patients with hormone-refractory prostate cancer (46, 47). Briefly, the primary objectives of these trials were to define the MTDs of the isotopes as well as to further define dosimetry, PK, and HAHA of the radiolabeled mAb conjugates. Anti-tumor responses were assessed as a secondary endpoint. The design and entry criteria of the 2 trials were identical. Eligible patients had a prior histologic diagnosis of prostate cancer and evidence of progressing recurrent or metastatic disease defined by at least 3 serially rising PSAs and/or radiographic studies. As prior studies had demonstrated that all prostate cancers were PSMA-positive (23), no determination of PSMA expression was done. Patients were required to have an absolute neutrophil count (ANC) $\geq 2.0 \times 10^9/L$, platelet count $\geq 150 \times 10^9/L$. Prior radiation therapy encompassing $> 25\%$ of the skeleton or prior treatment with ⁸⁹Strontium or ¹⁵³Samarium were not permitted. Other standard laboratory exclusion criteria applied as well (46, 47). Dose limiting toxicity in the 2 trials was defined as: Hematologic toxicity consisting of grade 4 thrombocytopenia (platelet $< 10 \times 10^9/L$) and/or grade 4 neutropenia (ANC $< 0.5 \times 10^9$) for greater than 5 days; and other toxicity consisting of grade ≥ 3 non-hematologic toxicity attributable to radiolabeled J591.

⁹⁰Y-J591 phase I trial:(46) Twenty nine subjects initially received 5 mCi of ¹¹¹In linked via a DOTA chelate to 20 mg of mAb J591 for pharmacokinetic and biodistribution determinations. One week later, they received ⁹⁰Y -DOTA-J591. All patients received 20 mg of mAb J591 with the ⁹⁰Y dose escalated in cohorts of 3 or more patients at the following planned dose levels: 5, 10, 15, and 20 mCi/m². A fifth dose level of 17.5 mCi/m² was added to more precisely define the MTD. Toxicity was dose-related and limited to reversible myelosuppression, predominantly thrombocytopenia. The 17.5 mCi/m² dose level was determined to be the MTD.

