Platelet nadir <25 x 10⁹/L occurred in 42% of pts, 9 of whom required 1 – 4 platelet transfusions (median = 2). 29/32 pts recovered normal platelet counts; the remaining 3 pts had rapidly progressive disease with bone marrow involvement. Neutropenia ≤ 0.5 x 10⁹/L occurred in 27% of pts, 6 of whom received brief therapy with growth factors. All 32 pts had normal neutrophil recovery and no pt experienced neutropenic fever. No significant drug-related non-hematologic toxicity has occurred. Excellent targeting of known sites of PC metastases has been observed in 31/32 (97%) of pts.

In summary, single dose ¹⁷⁷Lu-J591 demonstrates anti-tumor activity in pts with progressive CRPC with reversible myelosuppression. 32 of the initially planned 32 subjects have been treated to date and follow up is ongoing. Because of an FDA mandate, treatment was begun at a lower dose than the phase I MTD. Since there appears to be a dose response relationship (13 vs 47% with >30% PSA decline, 46 vs 71% with any PSA decline), an expansion protocol at the MTD is planned to tighten the confidence intervals for response at the MTD. Based upon acceptable toxicity in both groups and signals for increased efficacy at the higher dose (the MTD based upon the phase I trial), we are proceeding with the current trial.

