5.2.2.3 Neutropenia – growth factor guidelines

- Per ASCO guidelines (109), WBC growth factors are not recommended for afebrile neutropenia. However physicians may consider prophylaxis with filgrastim or pegfilgrastim for those subjects with severe neutropenia and known risk factors for neutropenic complications, including age > 65. Sargramostim (GM-CSF) should not be used because of its effect against

prostate cancer (110-114), including in combination with ketoconazole in this patient population (115).

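### Appendix B has no duration-only line for grade 4 neutropenia, so an afebrile episode of 14 to 30 days can trigger no mandatory DSMB notification (low severity, cheap to fix)

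*Combined protocol and SAP*

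**What the plan says.** Appendix B carries over the stopping rules of the earlier single-dose phase II trial. Its heading calls them a guideline for DSMB reporting, but the body is binding: "the DSMB must be notified when any of the below stopping rules occur". More than one such event among the first 9 subjects also holds enrollment (Appendix B and Section 12.4).

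The listed neutropenia events are:

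- "Grade 4 neutropenia that requires growth factor support for more than 14 days"
- "Grade 3 neutropenia that persists > 30 days"
- any febrile neutropenia.

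For platelets the same list has a duration-only grade 4 line, "Grade 4 thrombocytopenia that persists for ≥ 14 days after therapy", and a separate line based on transfusion need. The remaining catch-all covers non-hematologic toxicity only.

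On growth factor, Section 5.2.2.3 says that "WBC growth factors are not recommended for afebrile neutropenia", but adds that "physicians may consider prophylaxis with filgrastim or pegfilgrastim for those subjects with severe neutropenia and known risk factors", and it names age over 65 among those risk factors.

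**The concern.** The grade 4 neutropenia line puts its clock on the treatment and not on the neutropenia. In an afebrile man that treatment is discretionary and, as a default, not recommended. A long, deep, afebrile neutropenia can therefore pass without meeting any line, while a shallower episode of 31 days at grade 3 meets one. If one man has growth factor for 15 days and another with identical counts has it for 14 days or not at all, only the first must be notified to the DSMB.

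Myelosuppression is the expected major toxicity of 177Lu-J591 (Section 12.4). What is at stake is mainly the duty to notify the DSMB, which has no cohort limit and runs for the whole trial.

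**Working it through.** There is no stated figure to reproduce. The check is which episodes the list covers.

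**Reading of the lines.** Take g4 as days with ANC below 500, g3 as further days at grade 3, and GF as days of growth factor. *Grade 3* in the 30-day line is read as grade 3 or worse, which favors the plan; a literal reading would widen the gap. For an afebrile man:

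- growth-factor line: g4 > 0 and GF > 14
- 30-day line: g4 + g3 > 30.

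An episode with g4 of at least 14 days is therefore unlisted when g4 + g3 ≤ 30 and GF ≤ 14.

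| g4 | g3 | g4 + g3 | GF | Line met |
|---|---|---|---|---|
| 14 | 16 | 30 | 0 | none |
| 14 | 17 | 31 | 0 | 30-day line |
| 20 | 10 | 30 | 14 | none |
| 20 | 10 | 30 | 15 | growth-factor line |
| 20 | 16 | 36 | 0 | 30-day line |
| 25 | 10 | 35 | 0 | 30-day line |
| 30 | 0 | 30 | 0 | none |
| 31 | 0 | 31 | 0 | 30-day line |

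**Extent.** In whole days, the pairs (g4, g4 + g3) with 14 ≤ g4 ≤ g4 + g3 ≤ 30 number 17 × 18 / 2 = 153. Each allows GF from 0 to 14, which is 15 values, so 153 × 15 = 2,295 combinations meet no line. A line for grade 4 neutropenia of 14 days or more reduces this to 0. The count describes the shape of the gap; it is not a frequency.

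**Other routes to the DSMB.**

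- Section 12.3: adverse event tables at quarterly, semi-annual or annual review, and Study Chair updates. Neither is tied to an event.
- Sections 7.4.2 to 7.4.4: SAEs go to the IRB, the coordinating center and the FDA; the DSMB is not named. Blood dyscrasias are an example of an important medical event (Section 7.4.1), so classification is a judgment. The 24-hour rule in Section 7.4.3 names thrombocytopenia and bleeding as examples, not neutropenia, although the wording is open.

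None of these is an event-triggered DSMB notice for this episode.

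**Frequency.** In the prior phase II trial (Section 2.1), ANC of 0.5 or below "occurred in 27% of pts, 6 of whom received brief therapy with growth factors". The denominator of the 27% is not stated: 8/32 = 25% and 9/32 = 28%, so neither count out of 32 gives it. The number of neutropenic men who had no growth factor therefore cannot be recovered. No durations are given.

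If 27% is assumed to carry over, 34 men on 177Lu-J591 give 34 × 0.27 = 9.2, and two thirds of 55 give 36.7 × 0.27 = 9.9 with any ANC of 0.5 or below. That is a ceiling of about 9 to 10 men. The number in the gap lies between 0 and that ceiling.

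**The case against.** The strongest reply is that this list was not drafted carelessly. It reproduces criteria that the FDA required for the same agent in the prior phase II trial, and febrile neutropenia already triggers with no duration or growth-factor condition. What remains is an afebrile laboratory finding. All 32 phase II men recovered, none had neutropenic fever, and Section 12.4 expects toxicity here to be no worse. This stands and limits the severity. It does not explain why the platelet list counts grade 4 duration and the neutropenia list does not.

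A second reply is that 14 days has no neutropenia basis in the documents. That is right. The phase I trials counted grade 4 neutropenia "for greater than 5 days; and other toxicity consisting of grade" 3 or worse non-hematologic events as dose limiting, with no growth-factor condition. This is precedent for counting duration, but it served dose escalation and does not point to 14 days. The figure is borrowed from the platelet line and is more lenient than the phase I limit.

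Third, growth factor is not generally withheld. Age over 65 is a named risk factor, and the phase II median age was 71; if ages here are similar, many men could be considered for it. That is fair, but phase II use was described as brief, and use for 14 days or less still meets no line.

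A reader might infer that such an episode would go unseen. The documents do not support that. CBCs are at least twice weekly below ANC 500, cycle 3 results are due within 24 hours (Section 10.1), the Study Chair monitors in real time, the DSMB has periodic tables, and a Research Monitor can stop the study (Appendix D).

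**Conclusion.** The gap is real but narrow, and worth a cheap correction. In the bullet list, an afebrile grade 4 episode of 14 to 30 days, with total grade 3 or worse time of 30 days or less and growth factor for 14 days or less or none, triggers no mandatory DSMB notification. Its frequency is unknown and probably low. It does not affect the validity of the efficacy comparison.

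Two further inferences should not be drawn. The first is that the early enrollment hold is compromised: its review was expected by summer 2011 and this version cites a 2015 paper, so that stage is probably past. The second is that phase II men are known to have fallen in the gap: no durations are reported, so nothing shows this.

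The conclusion assumes that *Grade 3* means grade 3 or worse and that the bullets are the complete list. A figure under the Hematologic heading is not available in the text reviewed. Nothing suggests that it holds another criterion, but this cannot be ruled out.

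**What to change.** Add one line to Appendix B as a DSMB notification trigger: *Grade 4 neutropenia persisting ≥14 days, with or without growth factor support*. Define the duration over consecutive CBCs with ANC below 500 and no intervening value of 500 or more, so that separate dips are not joined into one episode. Keep the existing lines. If duration was left out on purpose, a sentence giving the reason would serve instead.

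The cost is a protocol amendment, possibly with FDA agreement because the list derives from FDA criteria, and perhaps a few more DSMB notifications. No new blood tests are needed: twice-weekly CBCs give about 2 × 2 = 4 results in 14 days. For men without the optional C2D22 count, the first required CBC after infusion is at C3D1, about 4 weeks later, so the recorded duration is a lower bound and some episodes may still be undercounted.

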Appendix C Calculation of % Skeleton Involvement*

*International Commission on Radiological Protection: Task Group on Reference Man. Report of the task Group on Reference Man: a report prepared by a task group of Committee 2 of the International Commission on Radiological Protection. Oxford; New York: Pergamon Press, 1975

Appendix D

Protocol Addendum

A Randomized Phase 2 Trial of ^{177}Lu Radiolabeled Monoclonal Antibody HuJ591 (^{177}Lu -J591) and Ketoconazole in Patients with High-Risk Castrate Biochemically Relapsed Prostate Cancer
After Local Therapy
IRB # 0810010067
HRPO Log Number A-15378

The following are reporting requirements and responsibilities of the Principal Investigator to the United States Army Medical Research and Materiel Command's (USAMRMC) Office of Research Protections (ORP), Human Research Protection Office (HRPO).

- (1) The protocol will be conducted in accordance with the protocol submitted to and approved by the USAMRMC ORP HRPO and will not be initiated until written notification of approval of the research project is issued by the USAMRMC ORP HRPO.**
- (2) Accurate and complete study records will be maintained and made available to representatives of the U.S. Army Medical Research and Materiel Command as a part of their responsibility to protect human subjects in research. Research records will be stored in a confidential manner so as to protect the confidentiality of subject information.**
- (3) All unanticipated problems involving risk to subjects or others, serious adverse events related to participation in the study and subject deaths related to participation in the study will be promptly reported by [contact]), by email ([contact]), or by [contact]) to the USAMRMC, Office of Research Protections, Human Research Protection Office. A complete written report will follow the initial notification. In addition to the methods above, the complete report will be sent to the U.S. Army Medical Research and Materiel Command, ATTN: MCMR-RP, [name].**
- (4) Suspensions, clinical holds (voluntary or involuntary), or terminations of this research by the IRB, the institution, the Sponsor, or regulatory agencies will be promptly reported to the USAMRMC ORP HRPO.**
- (5) Any deviation to the protocol that may have an adverse effect on the safety or rights of the subject or the integrity of the study will be reported to the USAMRMC ORP HRPO as soon as the deviation is identified.**
- (6) Major modifications to the research protocol and any modifications that could potentially increase risk to subjects will be submitted to the USAMRMC ORP HRPO for approval prior to implementation. All other amendments will be submitted with the continuing review report to the USAMRMC ORP HRPO for acceptance.**

(7) A copy of the approved continuing review report and the local IRB approval notification will be submitted to the USAMRMC ORP HRPO as soon as these documents become available. A copy of the approved final study report and local IRB approval notification will be submitted to the USAMRMC ORP HRPO as soon as these documents become available.

(8) The knowledge of any pending compliance inspection/visit by the FDA, OHRP, or other government agency concerning this clinical investigation or research, the issuance of Inspection Reports, FDA Form 483, warning letters or actions taken by any Regulatory Agencies including legal or medical actions and any instances of serious or continuing noncompliance with the regulations or requirements that relate to this clinical investigation or research will be reported immediately to USAMRMC ORP HRPO.

Guidance for the Requirement of a Medical Monitor

Per DoD Directive 3216.02, all greater than minimal risk studies require a Medical Monitor. The USAMRMC ORP HRPO also reserves the authority to require assignment of a Medical Monitor for those protocols assessed as presenting no greater than minimal risk to the subjects participating in the study.

Responsibilities of the Medical Monitor

The medical monitor is required to review all unanticipated problems involving risk to subjects or others, serious adverse events and all subject deaths associated with the protocol and provide an unbiased written report of the event. At a minimum, the medical monitor must comment on the outcomes of the event or problem and in case of a serious adverse event or death, comment on the relationship to participation in the study. The medical monitor must also indicate whether he/she concurs with the details of the report provided by the principal investigator. Reports for events determined by either the investigator or medical monitor to be possibly or definitely related to participation and reports of events resulting in death must be promptly forwarded to the USAMRMC ORP HRPO.

Please indicate the name of the medical monitor and the role they will have in this research study. This individual will be a qualified physician, other than the principal Investigator, not associated with this particular study, able to provide medical care to research subjects for conditions that may arise during the conduct of this study, and will monitor the subjects during the conduct of the study.

Research Monitor: [name]

Describe the specific role of the Research Monitor in this research study:

The Research Monitor is responsible to oversee the safety of the research and report observations/findings to the IRB of Record or a designated official. The Research Monitor will review all unanticipated problems involving risk to volunteers or others associated with the protocol and provide an unbiased written report of the event to the IRB of Record. The Research Monitor may discuss the research protocol with the investigators, interview human subjects, and consult with others outside of the study about the research. The Research Monitor shall have authority to stop the research protocol in progress, remove individual human subjects from the study, and take whatever steps are necessary to protect the safety and well-being of human subjects until the IRB can assess the monitor's report. The Research Monitor is responsible for promptly reporting their observations and findings to the IRB.

Appendix E

Radiographic Guidelines

This study is designed to include men without radiographic evidence of metastases with the primary endpoint of various measures of time to the development of radiographic appearance of metastatic disease. It is understood that there may be instances when the determination of lack of radiographic evidence of metastases may be equivocal. The following general guidelines should be followed:

Equivocal bony lesions on bone scan should be evaluated by X-ray, CT, or MRI. If the etiology of the bone scan lesion may be explained by another cause (e.g. fracture), the lesion will not be considered evidence of osseous metastatic disease.

In the case of borderline lymphadenopathy, every attempt should be made to obtain historical scans. Should the lesion be present and stable over time and unchanged despite biochemical progression and in the opinion of the investigator does not represent metastatic disease from prostate cancer, the lesion will not be considered evidence of metastatic soft tissue disease.

Equivocal lesions suspicious for metastatic disease should be biopsied if feasible.

Keeping the guidelines in mind, any equivocal lesion should be assessed by the PI and may be discussed with the study chair. Images may also be sent for central review (assuming written informed consent has been provided).

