11. MEASUREMENT OF EFFECT

11.1 Primary Endpoint: Proportion free of radiographically evident metastases at 18 months. Bone scans with <3 metastatic lesions should be confirmed with CT/MRI or a repeat scan >4 weeks after the initial scan. Should a subject require confirmatory scans, the date of radiographic progression will be the date of the initial scan showing suspicion of metastasis.

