12.4 Initial Safety Review

¹⁷⁷Lu-J591 has been shown to be safe at a dose of 70 mCi/m² in a phase I dose-escalation trial and a multicentered phase II trial. Because the major toxicity (myelosuppression) is at least in part due to the location of metastases (cortical bone and bone marrow), it is expected that the toxicity in this study population will not exceed that seen in the trials in metastatic CRPC. However, safety data will be monitored on a real-time basis by the Study Chair and shared with the core study investigators. Should there be > 1 subject experiencing a stopping rule as defined by agreement with the FDA during the conduct of the phase II trial in metastatic CRPC (see Appendix B) within the initial 9 subjects (approximately 6 subjects receiving ¹⁷⁷Lu-J591), enrollment will be halted pending DSMB review. Enrollment will continue without a pause during the ongoing safety analysis. Completion of initial safety review is anticipated to be completed in summer, 2011.

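### Equivocal lesions on post-infusion scans, which can decide the primary endpoint, are classified by investigators who see blood counts that can point to 177Lu-J591

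*Combined protocol and SAP*

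**What the plan says.** Section 11.1 defines the primary endpoint as "Proportion free of radiographically evident metastases at 18 months". Sections 12.3 and 13.1.1 describe the trial as double-blind, with 111In-J591 as the placebo.

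Appendix E governs doubtful findings. It states that "any equivocal lesion should be assessed by the PI and may be discussed with the study chair". I read the PI as the site PI, because the study chair is named separately. A borderline node that is stable over time is not counted if it "in the opinion of the investigator does not represent metastatic disease from prostate cancer". Central reading is optional: "Images may also be sent for central review", with no statement that it is blinded or binding. The only central reading stated without such an option is that of the J591 scans (Section 9.2.1.1.2), which are not the endpoint scans.

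Some rules limit discretion. Section 11.1 says: "Bone scans with <3 metastatic lesions should be confirmed with CT/MRI or a repeat scan >4 weeks after the initial scan". Section 10.1 requires a second scan to confirm bone-scan progression in the first 6 months. Appendix E calls for X-ray, CT or MRI of equivocal bone lesions, and for biopsy of suspicious equivocal lesions where feasible.

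On access to counts, Section 10.1 has all cycle 3 CBC results entered in the database or emailed within 24 hours. Section 12.4 says that "safety data will be monitored on a real-time basis by the Study Chair and shared with the core study investigators". Section 15 gives the study chair both safety assessment and assessment of treatment effect, and has co-investigators at the coordinating center help interpret scans. Nothing in the available text keeps counts from the person who classifies a lesion.

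**The concern.** Marrow suppression is the main expected toxicity of 177Lu-J591, and it comes before the endpoint calls. Section 5.2.2.1 puts the platelet nadir 4 to 5 weeks after infusion, within the weekly cycle 3 counts. The first scheduled post-baseline scans are at 6 months (Section 10, footnote 1). An investigator who has managed a man through a deep nadir may therefore have a strong idea of his arm when later asked whether a doubtful lesion is metastatic.

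With about 34 and 17 men, few calls are needed to matter. If knowledge of the arm makes a reader slower to call metastasis in men thought to have had 177Lu, the comparison tilts toward the experimental arm, and the one-sided 10% test no longer has its stated error rate.

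**Working it through.** **Inputs.** Arm sizes 34 and 17, 18-month proportions 80% and 50%, one-sided alpha 10% (Section 13.1). Platelet nadir below 25 x 10^9/L in 42% (Section 2.1, phase II trial, 65 and 70 mCi/m2 cohorts together). The share of endpoint calls that are equivocal and the size of any reader bias are not in the documents and are assumed below.

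**1. The plan's power.** Pooled proportion = (34 x 0.8 + 17 x 0.5)/51 = 0.70.
- Null SE = sqrt(0.70 x 0.30 x (1/34 + 1/17)) = 0.1361.
- Alternative SE = sqrt(0.16/34 + 0.25/17) = 0.1393.
- z = (0.30 - 1.2816 x 0.1361)/0.1393 = 0.901, so power is 81.6%, in line with the stated 80% or more.

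Exact enumeration of the same pooled z-test gives power 82.4% and, at 50% versus 50%, type I error 9.97%.

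**2. What a deep nadir reveals.** With 2:1 allocation and f the share of 111In men who reach the same nadir, P(177Lu given nadir) = (2/3 x 0.42)/(2/3 x 0.42 + 1/3 x f). For assumed f of 0%, 1% and 5% this is 100%, 98.8% and 94.4%.

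**3. What its absence reveals.** Men on 177Lu without the nadir: 0.58 x 34 = 19.7. Taking all 17 controls as without it, P(control given no nadir) = 17/(17 + 19.7) = 46%. That does not identify a control.

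**4. Effect on type I error.** Assume no true effect (50% in both arms), control calls correct, a deep nadir unrelated to the true outcome, and a fraction m of the events in the recognised 42% called non-metastatic. The apparent 177Lu proportion is 0.5 + 0.5 x 0.42 x m. Rejection probability is the sum of binomial probabilities over all outcomes where the pooled z exceeds 1.2816.

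| m | apparent 177Lu proportion | type I error |
|---|---|---|
| 0 | 50.0% | 10.0% |
| 10% | 52.1% | 12.7% |
| 20% | 54.2% | 15.9% |
| 30% | 56.3% | 19.6% |

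In men: 34 x 0.5 = 17 events in the 177Lu arm, of which 0.42 x 17 = 7.1 are in recognised men. So m of 10%, 20% and 30% means about 0.7, 1.4 and 2.1 men. One reclassified 177Lu man moves that arm by 1/34 = 2.9 points.

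**5. If the reader cannot tell the arms apart.** Missing the same share of true events in both arms leaves type I error at 10.0%. Power falls from 82.4% to 80.2%, 77.8% or 72.5% when 5%, 10% or 20% are missed. Equal error costs power but does not favor an arm.

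**The case against.** The case on the other side has several sound parts.

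- **The 42% is borrowed.** It comes from men with metastases and pools two doses. Section 12.4 links marrow toxicity partly to where metastases lie, and expects no more of it here than in the metastatic trials. The rate could be lower; since all 177Lu men here are assigned the higher of the two doses, it could also move the other way. This stands, so 42% is used as an illustration.
- **111In is not shown to spare the marrow.** The heading of Section 7.1.1 can be read as no risks beyond those listed, and Section 13.1.1 speaks of treatment effect. Hence the assumed range of 0% to 5%.
- **Safeguards exist.** Confirmatory imaging and biopsy reduce the number of calls left to opinion. They do not blind whoever makes the remaining ones. Biopsy depends on feasibility, and the node rule includes investigator opinion.
- **Appendix E also serves eligibility.** Baseline calls precede the infusion, so counts cannot unblind them. The point is confined to post-infusion scans.

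A reader might also infer a much larger swing: two men in each arm reclassified in opposite directions gives 2/17 + 2/34 = 17.6 points against a 30-point target. The documents do not support this. Of that total, 11.8 points come from controls, and step 3 shows that lack of a deep nadir leaves a man slightly more likely to be on 177Lu than a control. Milder falls in counts may carry some information, but the documents give no figures for them.

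**Conclusion.** The point holds as a preventable exposure to bias. The final say on an equivocal post-infusion lesion rests with people who can see a strong, though partial, marker of the 177Lu arm, and the plan neither blinds that decision nor makes central review binding. Under the stated assumptions the false-positive risk moves from 10.0% to between 12.7% and 19.6%, for roughly one to two men called differently. These figures depend on the 42% rate carrying over, on a 50% event rate in both arms, and on assumed shares of events called away.

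A reader might infer that the trial is effectively unblinded or that its result will be biased. The documents do not show that: they give no rate of equivocal lesions and no evidence of how readers would act, and at the 42% rate 58% of 177Lu men would not have a platelet nadir below 25 x 10^9/L. The change is worth making because it is cheap, not because bias has been demonstrated.

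**What to change.** Apply the following to post-infusion scans only.

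1. In Appendix E and Section 11.1, state that lesion status follows the radiologist or nuclear physician who already reports the scan. That reader has no access to CBC, transfusion or adverse event data, and did not handle that man's J591 dose or J591 scan. The second condition matters because Section 5.1.3 gives the two labels very different activities (70 mCi/m2 versus 5 mCi) and Section 15 has nuclear medicine staff administer the agents and oversee the J591 scans. Results of the confirmatory imaging or biopsy already provided for override an equivocal read. The PI and study chair may request confirmation but do not decide status.
2. Record equivocal status and the original radiology report in the CRF, and pre-specify two sensitivity analyses of the 18-month proportion. The first counts every unresolved equivocal lesion, unless explained by another documented cause or by biopsy, as metastasis from first suspicion in both arms. The second uses the original radiology report, with the coding of a report that itself reads equivocal fixed in advance.

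Cost: the PI loses the final say on these lesions, a CRF field is added, and two analyses are run. A site where one nuclear physician covers both the J591 work and the bone scans would need a colleague to read the latter. No scans are added and the sample size is unchanged.
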